Azathioprine is first converted to 6-mercaptopurine in the liver. In red blood cells, hypoxanthine guanine phosphoribosyltransferase (HPRT) converts 6-mercaptopurine to 6-thioninosine-5' monophosphate, which is then converted to either 6-thioguanine nucleotides (6-TG) or 6-methyl-mercaptopurine ribonucleotides (6-MMP). 6-TG is the metabolite that is associated with immunosuppression, and thus may help decrease disease activity and lead to or maintain remission in IBD (Belaiche et. al, 2001, p. 72). It has a long half-life in red blood cells and other tissues. Thus, prolonged treatment is needed for it to accumulate to steady-state levels (p. 72). 6-TG is also cytotoxic and associated with suppression of bone marrow at levels greater than 400 pmol/8x10⁸ RBC (MacDermott, 2016). However, levels between 230 and 400 pmol/8x10⁸ RBC seem to be optimal for treating IBD and achieving remission. The other end metabolite of azathioprine/6-mercaptopurine, 6-MMP, is associated with hepatotoxicity at levels greater than 5700 pmol/8x10⁸ RBC (MacDermott, 2016). If thiopurine methyltransferase (TPMT) is deficient, bone marrow toxicity can occur due to elevated levels of 6-TG nucleotides. Thus, it is important to monitor the metabolism of azathioprine and 6-mercaptopurine through the levels of 6-TG and 6-MMP.

Methods

Research design: The study will be a prospective study in a cross over design, with each patient acting as a control for him/herself. Subjects will be patients contacted from a Rush University Medical Center database that are currently prescribed azathioprine and/or 6-mercaptopurine. They will be asked to take their medication at a determined time each day (morning or evening), complete questionnaires, and come in to get labs drawn. Data obtained will be analyzed according to statistical methods listed below in order to determine significance of association.

Power and Sample Size: There have been no prior studies testing the role of chronotherapy and IBD, therefore no knowledge exists on the anticipated effect. We aim for a prospective study to offer enrollment to all subjects who meet the study qualifications. For a mean difference of 5% and standard deviation of 20, we calculated that we will need to enroll 128 subjects to provide a power of 80% for a significance level of $\alpha=0.05$.

Inclusion Criteria: Patients with IBD who have taken, or are currently taking, azathioprine or 6-mercaptopurine.

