Exclusion Criteria: 1) Subjects who cannot give informed consent, 2) vulnerable populations including subjects < 18 years old, pregnant women, prisoners, non English-speaking and cognitively impaired individuals, 3) breastfeeding subjects, 4) patients treated with dual corticosteroid and immunomodulator therapy 5) patients who have had a history of complications related to immunomodulator therapy

Subject Consenting and Recruitment: Potential subjects will be identified through a Rush University Medical Center Database, and contacted via telephone. Subjects will also be recruited during their scheduled clinic appointments with Rush University Gastroenterologists. A newsletter will also be posted on rush.edu/clinical-trials for patients to identify whether they would be interested in the study. A study staff member will explain the study to them. If the subject meets study qualifications and they are interested, they can choose to have the consent

form physically mailed or emailed to them (if they were recruited by telephone). If they were recruited during a scheduled clinic appointment, they can sign the consent form or take it home and return it by mail. The PI, co-investigators, and other key study personnel will obtain the consent from the subjects using an IRB-approved consent form for participation in the study. They will also answer any questions that the subjects may have regarding the study. Subject participation is voluntary. Consent will be obtained by having the subjects sign either a paper copy or an online copy of the approved consent form in a private setting. Subjects are allowed to take the consent form home to review it on their own time.

Early Withdrawal: Subjects can withdraw from the study at anytime upon their request.

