All power estimates were computed using R package pwr, and we assume a Type I error rate of 0.05 and a 2-sided test for all analyses. Power estimates were derived from the data from prior unpublished studies. The primary endpoint of this study will be metabolites of 6-mercaptopurine. For Aim 1, previous studies have found that circadian enzymes can alter metabolites about 12% by different circadian controlled genes. With 128 UC subjects and effect size of 0.1 this will give us a 98% power to detect a difference in serum metabolites with a paired Wilcox Signed Rank test at alpha=0.05 level, and 84% power if gender is used as an independent variable. These conservative estimates provide a good estimate of the power to detect differences in metabolites chronotherapy in IBD patients. We anticipate we will have nonparametric data and will use the Wilcoxon match-pair test for analysis for inflammatory cytokines. This will be a nonrandomized trial that will not control for order effects, but other factors that are recorded such as cigarette smoking will be used as a covariate in multivariate analysis with analysis of variance (ANOVA) and linear regression as indicated. For Aim 2, a validated chronotype questionnaire (Munich Chronotype Questionnaire) will be compared optimal 6-mercaptopurine. Corrected midpoint of sleep will then be compared to 6-MP metabolites to see if chronotype impacts metabolite profiles. Data will be presented as median \pm range for variables that can be considered nonparametric. All analyses will use R (v.3.2.5) and SPSS (SPSS Inc., Chicago, IL).

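### The 98% power stated for the primary metabolite endpoint does not follow from its stated inputs: as a standardised paired difference, 0.1 with 128 pairs gives about 20%, and the 84% figure cannot be reproduced

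*Combined protocol and SAP*

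**What the plan says.** The Study and Data Analysis section names metabolites of 6-mercaptopurine as the primary endpoint, sets a two-sided 5% level for all analyses and says that all power estimates came from the R package pwr. For a paired Wilcoxon signed-rank test it states: "With 128 UC subjects and effect size of 0.1 this will give us a 98% power to detect a difference in serum metabolites". It adds "84% power if gender is used as an independent variable". On where the inputs come from, it says "Power estimates were derived from the data from prior unpublished studies" and "previous studies have found that circadian enzymes can alter metabolites about 12% by different circadian controlled genes". It concludes: "These conservative estimates provide a good estimate of the power to detect differences in metabolites".

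The Power and Sample Size paragraph under Methods has a separate statement: "For a mean difference of 5% and standard deviation of 20, we calculated that we will need to enroll 128 subjects", for 80% power at alpha 0.05. It names no endpoint and no test. The same paragraph says: "There have been no prior studies testing the role of chronotherapy and IBD, therefore no knowledge exists on the anticipated effect".

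No section defines the scale of 0.1, gives a standard deviation for paired metabolite differences, or describes the calculation behind the 84%.

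**The concern.** An effect size of 0.1 given without units, next to a paired test and a power package, is most naturally read as a mean paired difference divided by its standard deviation. On that scale 0.1 is a small effect, and 128 pairs cannot come near 98% power for it.

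This is the only power statement tied to the named primary endpoint, and the plan calls it conservative. If the figure is wrong, or rests on inputs nobody can see, a reader cannot tell what metabolite difference the study is able to detect. A null metabolite result could then be taken as strong evidence of no effect when it might be nothing of the kind.

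**Working it through.** **Inputs.** From Study and Data Analysis: n = 128 subjects, effect size 0.1, two-sided alpha 0.05, paired signed-rank test, stated power 98% (84% with gender), expected change about 12%. From Power and Sample Size: difference 5%, SD 20, n = 128, power 80%. Each subject is his or her own control, so 128 subjects make 128 pairs.

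**Formula.** For a standardised paired difference d, the paired t statistic is noncentral t with n − 1 degrees of freedom and noncentrality d√n. Power is the probability that it exceeds the two-sided 5% critical value in absolute size.

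**1. The statement that reproduces.** d = 5/20 = 0.25 gives noncentrality 0.25 × √128 = 2.83 and power 80.2% with 128 pairs (79.8% with 127). The Power and Sample Size figure is therefore what a standardised paired calculation yields.

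**2. The 98% on the same scale.** d = 0.1 gives noncentrality 0.1 × √128 = 1.13 and power 20.2%. By hand, Φ(1.13 − 1.96) = Φ(−0.83) ≈ 0.20.

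**3. The planned test.** Signed-rank power by simulation (20,000 runs, n = 128, differences scaled to SD 1; simulation error about 0.3 points near 20%):

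| Shape of differences | d = 0.10 | d = 0.25 |
|---|---|---|
| Normal | 19.8% | 78.4% |
| Laplace | 28.3% | 91.1% |
| t, 3 df | 34.1% | 96.6% |

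The last row is not a ceiling: t with 2.5 df gives about 48% at d = 0.1. None of these approaches 98%.

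**4. What 98% needs with 128 pairs.** By paired t, d = 0.3575. By signed-rank, about 0.37 with normal differences and about 0.27 with t on 3 df.

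**5. Other scales for 0.1.**
- Correlation of 0.1: about 20%.
- Regression f² of 0.1: 94.4%, 89.6%, 85.3% and 81.4% with one to four predictors. This matches neither 98% nor 84%, and it is not a paired effect size.
- Raw 10% change: 98% needs an SD of paired differences of 10/0.3575 = 28.0. For the cited 12% it needs 12/0.3575 = 33.6. Neither SD is stated. The only SD in the documents is 20, attached to no endpoint. Used as the SD of differences, it gives d = 10/20 = 0.5 and power over 99.9%, which is not 98% either.
- 0.1 on the per-occasion SD with within-subject correlation ρ: the paired d is 0.1/√(2(1 − ρ)). Setting this to 0.3575 gives 1 − ρ = (0.1/0.3575)²/2 = 0.039, so ρ ≈ 0.96. No section gives a correlation.

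**6. The 84%.** It would fit, for instance, a standardised difference of 0.375 in 64 pairs. The plan states no such effect or split, so this is a guess and not a reproduction.

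**The case against.** The strongest defence is that 0.1 means a 10% change and not a standardised effect. Take the SD of 20 as a per-occasion value and assume the two occasions are uncorrelated. The SD of differences is then 20 × √2 = 28.3, and power is 97.8%, in effect the stated figure. This stands as a possibility, and it is why 98% cannot be called impossible. But it borrows an SD that is not tied to metabolites and adds a zero correlation that appears nowhere. On the same assumptions, the 5% difference in Power and Sample Size would have 51% power, not 80%. The per-occasion scale with ρ near 0.96 is equally possible and equally undocumented.

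A second defence is that the enrolment target has its own calculation, which reproduces. That is true, and it limits the consequence. It does not replace the missing support for the primary endpoint, because that calculation names no endpoint.

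Two stronger readings are tempting and not supported:
- A reader might infer that the two sections contradict each other because 128 subjects carry 80% power in one and 98% in the other. Under normal theory no single SD of paired differences fits both 80% at 5% (SD 20.0) and 98% at 10% (SD 28.0). But nothing says the two statements concern the same variable, so a conflict is not shown.
- A reader might infer that having no knowledge of the effect contradicts having unpublished data. The first statement is about chronotherapy studies in IBD, and the second may refer to other circadian work. Both can be true. What remains is that no figures from the unpublished data are given.

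**Conclusion.** The point holds. The stated inputs do not deliver the stated 98%. With 0.1 as a standardised paired difference, power is about 20% (paired t 20.2%; signed-rank 19.8% with normal differences, 28.3% Laplace, 34.1% t with 3 df). The 98% can be right only if the documents omit a decisive input: an SD of paired differences near 28 for a raw 10% change, or a within-subject correlation near 0.96 for 0.1 on the per-occasion scale. The 84% cannot be checked at all. Calling these estimates conservative has no visible basis.

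The 20% depends on the standardised reading. That reading is supported by the unitless label and by the other sample-size statement reproducing on that scale, but it is not confirmed. A reader might go further and infer that the study truly has 20% power, or that it must grow to the 1,613 pairs that 98% at d = 0.1 would need by paired t. The documents do not support either inference: the fault may lie in the effect-size label and not in the power, and without the scale and the SD the adequacy of 128 cannot be judged.

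**What to change.** In Study and Data Analysis, state the scale of 0.1, the SD of paired metabolite differences with its source in the unpublished studies, and the model, effect and gender split behind the 84%. Then replace 98% and 84% with the power those inputs give for the planned signed-rank test, naming the distribution assumed for the differences. In Power and Sample Size, name the endpoint and test to which the 5% and the SD of 20 apply.

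If no documented inputs support the two figures, delete both, together with the word conservative, and write:

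*128 evaluable pairs give about 78% power for a standardised paired difference of 0.25 and about 20% for 0.1 (signed-rank test, normal differences, two-sided alpha 0.05; paired t 80% and 20%).*

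The 0.25 should not be presented as the metabolite effect unless the investigators confirm that the Power and Sample Size figures refer to metabolites.

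The cost is a change of wording and one recalculation. The stated power may become less favourable. No change in enrolment is proposed.

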Description of Procedures: After signing the informed consent form, subjects will be asked to answer the Inflammatory Bowel Disease Questionnaire (IBDQ), the Munich Chronotype Questionnaire (MCTQ), the Owl and Lark Questionnaire, the Harvey Bradshaw questionnaire, the RU SATED questionnaire, and a demographics survey. All six of these questionnaires are included with this IRB. Next, patients will be assigned a time (morning or evening) to self-administer their prescribed medication for 10 weeks. Patients who currently take their medication in the morning will be asked to switch to an evening delivery and patients who currently take their medication at night will be asked to switch to a morning delivery. The group assigned to morning delivery time will be told to take their medication between 6am and 11am. The group assigned to evening delivery time will be told to take their medication between 6pm and 11pm. Lastly, patients will be asked to give a blood sample to test for complete blood count (CBC), comprehensive metabolic panel (CMP), C-reactive protein (CRP), methylmercaptopurine (6-MMP), and thioguanine nucleotides (6-TG). Plasma and serum isolated from the blood sample will be temporarily stored to measure inflammatory cytokines after every 20 subjects complete the study.

Within a 6-10 week window, as part of their clinical care, subjects will come in to assess their clinical status while undergoing biochemical monitoring every 2-4 weeks. Data from their endoscopic examination, if done, will also be collected.

After 10 weeks, the subjects will be asked to complete the IBDQ and Harvey Bradshaw questionnaire. In addition, a blood sample will be obtained to measure the same metabolite levels and other biochemical indications of disease as stated above. Again, plasma and serum will be isolated from the blood sample and stored.

Study Design Flow:

Subjects on azathioprine or 6-mercaptopurine from Rush database that satisfy inclusion criteria recruited for study and consented

Questionnaires administered: IBDQ, Owl and Lark, Harvey Bradshaw, MCTQ, SATED,
demographics
Blood draw

Morning or evening group for delivery based on previous time of medication administration

After 10 weeks: Re-administer Harvey Bradshaw and IBDQ surveys and a second blood draw

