Our study is based on the potential circadian oscillation of the enzymes responsible for metabolizing IMs (as above), as well as that of the pro- and anti-inflammatory cytokines also described above. The oscillatory nature of these enzymes and cytokines may differ amongst individuals based on their circadian makeup, which we hope to assess via the chronotype surveys (Owl and Lark, MCTQ, RU SATED). We will assess the potential benefit of taking IMs in the morning vs evening by assessing changes in clinical outcomes, laboratory data, endoscopic findings/imaging (if subjects undergo a colonoscopy or imaging as part of their standard care while a part of this study), and quality of life surveys (Harvey Bradshaw, IBDQ). The study is a prospective cross-over study in which each patient is assigned to the morning or evening group based on when they currently take their medication. Therefore, each subject serves as his/her own control.

Study Outcomes: The goal of this study is to determine whether time of delivery of medication affects the efficacy or side effects of this medication. The study outcomes include 1) IBD clinical status as either a) remission defined per no need for step-up therapy (steroid, initiation of anti TNF, change of TNF, or surgery), or b) complications (fistula or abscess) 2) changes in the IBDQ and Harvey Bradshaw questionnaires.

Expected Outcomes: The expected outcome of this study is that there will be a difference seen in disease outcomes for IBD between the different groups based on what time they are taking their medication. Based on the known enzymatic pathways of IM metabolism and their potential circadian rhythm, we expect to see variation in the efficacy as well as toxicity of IMs when administered at different times of the day. Understanding these variations and determining the predicting factors (e.g., chronotypes) can lead to circadian-based administration of IMs to increase the efficacy of the drug while minimizing its side effects. We expect to see differences in the IBD quality of life questionnaire and the Harvey Bradshaw questionnaire from before the intervention to after the intervention, as well as differences in clinical disease activity as determined by levels of metabolites, endoscopic findings, and imaging, between the two groups.

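### The paired metabolite difference is undefined and order effects are left uncontrolled, so a ten-week drift common to all patients can enter the morning-versus-evening contrast

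*Combined protocol and SAP*

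**What the plan says.** Study and Data Analysis makes metabolites of 6-mercaptopurine the primary endpoint. The only test it attaches to them appears in the power statement: "to detect a difference in serum metabolites with a paired Wilcox Signed Rank test". It does not define the paired difference. It then says: "This will be a nonrandomized trial that will not control for order effects". The same sentence offers ANOVA and linear regression with other recorded factors as covariates. Smoking is the only one named, and switch direction is not mentioned.

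Direction follows habit. Under Description of Procedures, "Patients who currently take their medication in the morning will be asked to switch to an evening delivery", and evening takers do the reverse. Study and Data Analysis repeats that "each patient is assigned to the morning or evening group based on when they currently take their medication". There is one blood draw before the switch and one after ten weeks. No quota or expected split is given.

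Two other statements bear on the contrast. The benefit is to be judged for "taking IMs in the morning vs evening by assessing changes in clinical outcomes, laboratory data", which joins a clock-time comparison to a before-after one. Expected Outcomes anticipates "differences in clinical disease activity as determined by levels of metabolites, endoscopic findings, and imaging, between the two groups", but no test is assigned to that comparison.

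**The concern.** With patients switching in both directions, morning minus evening and week 10 minus baseline are different quantities. For a patient who moves from evening to morning they coincide; for one who moves from morning to evening they have opposite signs. The signed-rank test therefore answers a different question under each choice, and the plan does not make the choice.

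Within each direction, dosing time and visit are completely confounded. Anything that shifts metabolites over ten weeks, whatever the clock time, enters the paired difference. In the clock-time contrast it cancels only if the two directions are equally represented. The trial exists to ask whether dosing time matters, and an uncancelled drift can create such an effect or hide one, depending on its sign.

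Drift is possible on the plan's own account. For 6-TG, "prolonged treatment is needed for it to accumulate to steady-state levels", yet no minimum time on the drug is required at entry. Clinical monitoring every 2-4 weeks continues during the study, and the Background links such monitoring to dose adjustment. Instructed dosing windows apply only after the switch.

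**Working it through.** **Inputs.** From Power and Sample Size: mean difference 5, SD 20, n = 128, power 80%, α = 0.05. Study and Data Analysis makes the tests two-sided. The sample-size sentence names no endpoint and does not say what the SD refers to; I take it as the SD of within-patient change. P and p are not in the documents and are shown as ranges.

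**Plan's figure.** A paired t-test with standardised difference 5/20 = 0.25 and n = 128 has power 80.2%, so 128 reproduces under that reading of the SD. The separate 98% power figure in Study and Data Analysis is not used here.

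**Estimands.** The expected week-10-minus-baseline change is P − d for morning-to-evening patients (share p) and P + d for evening-to-morning patients (share 1 − p).

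- By clock time (morning minus evening): p(d − P) + (1−p)(d + P) = d + (1−2p)P.
- By visit (after minus before): p(P − d) + (1−p)(P + d) = P + (1−2p)d.
- Half the difference in mean change, evening-to-morning minus morning-to-evening: d, for any p.

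**Size of the clock-time bias.** With |P| = 2.5 it is 0.4 × 2.5 = 1.0 at 70:30 and 0.6 × 2.5 = 1.5 at 80:20, against a planning difference of 5.

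**Rejection rates.** Simulation with n = 128, normal errors, SD 20, groups of 64:64, 77:51, 90:38 and 102:26, the majority switching morning to evening; 20,000 runs per cell, two-sided 0.05.

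| Scenario | 50:50 | 60:40 | 70:30 | 80:20 |
|---|---|---|---|---|
| Clock-time signed-rank, d = 0, P = 1 | 5% | 5% | 5% | 6% |
| Same, P = 2.5 | 5% | 6% | 9% | 13% |
| Same, P = 5 | 4% | 8% | 19% | 36% |
| Direction-adjusted rank-sum, d = 0, any common P | 5% | 5% | 5% | 5% |
| Direction-adjusted rank-sum, d = 5, any common P | 78% | 76% | 71% | 60% |

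At 70:30 with d = 5, clock-time power is about 78% for P = 0, 58% for P = +2.5 and 91% for P = −2.5.

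The by-visit test rejects about 28% of the time at P = 2.5 and 79% at P = 5 with no timing effect, at every split. With d = 5, no drift and a 50:50 split, it rejects only 4-5% of the time.

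**Unequal drift.** Let the drift be Pme in morning-to-evening and Pem in evening-to-morning patients, with mean P̄ and G = Pem − Pme. Clock time then estimates d + (1−2p)P̄ + G/2, and the half-difference estimates d + G/2. At p = 0.7:

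| Pme, Pem | Clock-time bias | Adjusted bias |
|---|---|---|
| 5, 5 | −2.0 | 0 |
| 0, 5 | +1.5 | +2.5 |
| 5, 0 | −3.5 | −2.5 |

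With d = 0 at 70:30, drift of 5 only in evening-to-morning patients gives 12% false positives for clock time against 24% adjusted. Drift of 5 only in morning-to-evening patients gives 48% against 24%.

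**The case against.** The clock-time reading has good support. The primary objective and three of the four specific aims ask about morning versus evening, and the design is called a cross-over with each patient as his or her own control. The before-to-after wording in Expected Outcomes concerns the questionnaires, not the metabolites. This stands: a reader might infer that the plan intends a by-visit test, and the documents do not support that. The difference is still undefined, however, and the clock-time reading still carries (1−2p)P.

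The lack of order control is disclosed. It is, but disclosure neither defines the contrast nor removes the bias. The covariate list is open, yet the sentence sets order apart from the covariates, and adjusting for smoking does not remove P.

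Large drift is unlikely. Research design draws on patients "that are currently prescribed azathioprine and/or 6-mercaptopurine", the Background says immunomodulators are continued long term, and Safety and Adverse Events says dose and frequency are not altered by the study. Dose adjustment can also go either way from patient to patient. This stands as a limit on size; at P = 1 the effect on false positives is negligible.

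Adjustment is a trade-off. With P = 1, the clock-time mean squared error at 70:30 is 400/128 + 0.41² = 3.29, against 1.93² ≈ 3.74 for the half-difference. Direction is self-selected, so unequal drift is a real possibility, and the adjusted analysis can then be the worse one. This also stands. It argues for pre-specifying both analyses, not for neither.

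**Conclusion.** The point holds as a defect of specification with a conditional consequence. The primary paired difference is undefined. Under the better-supported reading, the timing contrast is free of common drift only with an even split or no drift, and the plan secures neither. The algebra needs no assumed values beyond a drift common to both directions. The percentages assume normal changes with SD 20 and chosen values of P and p.

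Three stronger readings are not supported. A reader might infer that the trial's result will be biased; the documents give neither drift nor split, so the size is unknown and may be slight. A reader might infer that an even split is a safeguard in general; it protects only clock-time subtraction, and under by-visit subtraction it leaves drift alone. A reader might infer that a gap between the clock-time and direction-adjusted estimates would reveal drift. It would not: with no drift at all the gap is at least 1.0 in about 20% of trials at 70:30 and 44% at 80:20, it is always zero at 50:50 for means, and it says nothing about G.

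This should be fixed before the data are examined, because choosing the subtraction afterwards would permit selective reporting.

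**What to change.** 1. In Study and Data Analysis, define the metabolite difference as morning minus evening, and use the same contrast for cytokines, IBDQ and Harvey Bradshaw.
2. Pre-specify a direction-adjusted analysis alongside it: compare week-10-minus-baseline change between evening-to-morning and morning-to-evening switchers by rank-sum test, with half the Hodges-Lehmann difference and its 95% CI estimating d. Report both analyses and the observed split, and say in advance which one carries the conclusion.
3. Replace the statement that order effects are not controlled with wording such as: the direction-adjusted analysis removes a period effect common to both switch directions; because direction is set by habit, a difference in drift G between the groups is not removed and biases the estimate by G/2. Add that a gap between the two estimates will not be taken as proof of drift.

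**Cost.** There are no new visits or blood draws, and switch direction is already known from assignment. Keep n = 128 and state the adjusted rank-sum power for d = 5, SD 20: about 78/76/71/60% at 50:50/60:40/70:30/80:20. The clock-time test has about 78% at every split if drift is nil, so the adjustment costs about 7 points at 70:30 and 18 at 80:20. Holding the adjusted analysis at the planned power would instead need about 128/(4p(1−p)) patients: 128/0.84 ≈ 153 at 70:30 and 128/0.64 = 200 at 80:20. The plan should also say that the adjusted analysis can be the worse of the two under unequal drift.

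### Median plus-or-minus range is the only reporting rule for the main outcomes; no paired estimate or confidence interval is named, so the trial's precision would not be shown

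*Combined protocol and SAP*

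**What the plan says.** Four parts of the combined protocol and SAP bear on this.

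- **Design.** Methods, Research design, describes a crossover "with each patient acting as a control for him/herself". Each patient contributes one set of values under the usual dosing time and one after 10 weeks at the other time.
- **Endpoint and tests.** Study and Data Analysis states: "The primary endpoint of this study will be metabolites of 6-mercaptopurine". It claims power to "detect a difference in serum metabolites with a paired Wilcox Signed Rank test at alpha=0.05 level", and adds: "We anticipate we will have nonparametric data and will use the Wilcoxon match-pair test for analysis for inflammatory cytokines".
- **Presentation.** The same section gives one rule for displaying results: the median plus or minus "range for variables that can be considered nonparametric".
- **Planning effect.** Power and Sample Size says: "For a mean difference of 5% and standard deviation of 20", "we will need to enroll 128 subjects to provide a power of 80" per cent. Study and Data Analysis adds a 12% change in metabolites and an effect size of 0.1.

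No section names a confidence interval, a standard error, a Hodges-Lehmann estimate or a median paired difference as something to report.

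**The concern.** The rule is limited to nonparametric variables, but the plan tests its primary metabolites and its cytokines by signed-rank methods, so the main results fall under it. It has two defects.

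First, a range is the distance between the two most extreme patients. It is not symmetric about the median, so adding it to and subtracting it from the median has no clear meaning. It also widens as patients are added, whereas a measure of precision narrows.

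Second, medians at the two dosing times discard the pairing. The difference between them is not what the signed-rank test addresses, and the two can disagree in sign.

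The study asks whether dosing time matters, so the size of the within-patient difference is the answer. If the result is not significant, a reader given only medians and ranges cannot tell whether an effect of the planned size has been excluded or is still open.

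**Working it through.** **Inputs.** Difference 5, SD 20, N 128 and power 80% come from Power and Sample Size. For the significance level, Study and Data Analysis says "we assume a Type I error rate of 0.05 and a 2-sided test for all analyses". The text does not say what the SD of 20 refers to.

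**Step 1: reproduce the plan's N.** Treat 20 as the SD of paired differences.
- Normal approximation: n = (20 × (1.960 + 0.842) / 5)² = 125.6, so 126.
- Exact paired t-test: n = 128, with power 80.2%.
- Two independent groups would need 252 per group, 504 in all.

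The stated 128 therefore matches the paired reading.

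**Step 2: precision with 128 pairs.**
- Standard error = 20 / √128 = 1.768.
- 95% half-width = t(0.975, 127) × 1.768 = 1.979 × 1.768 = 3.50 points, so the full width is 7.0.
- The Hodges-Lehmann interval, simulated on normal differences, has a half-width of about 3.6.

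**Step 3: what the range would show.** The simulated mean range of 128 normal values with SD 20 is about 104 points (95% of samples: 83 to 130). At 64 values it is about 94, so it grows with n. Full width against full width, 104 / 7.0 is about 15. This is illustrative: it assumes normality and uses the SD of differences, because the documents give no SD for raw levels between patients.

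**Step 4: when the interval excludes the target.** It excludes both +5 and −5 if the estimate lies within 5 − 3.50 = 1.50 of zero. With no true effect, the probability is 2Φ(1.50 / 1.768) − 1 = 2Φ(0.85) − 1, about 60%. The simulated Hodges-Lehmann interval gives about 56%.

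**Step 5: sensitivity.** Completer numbers below 128 and SDs other than 20 are assumptions; the plan states no dropout rate. The last column is simulated for the t interval.

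| SD of differences | Pairs | Half-width | Chance of excluding ±5, no true effect |
|---|---|---|---|
| 20 | 128 | 3.50 | 60% |
| 20 | 102 | 3.93 | 41% |
| 20 | 90 | 4.19 | 30% |
| 20 | 64 | 5.00 | 6% |
| 25 | 128 | 4.37 | 22% |
| 28.3 | 128 | 4.95 | 5% |

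The last row is the case where 20 is the SD of a single measurement and the two measurements are uncorrelated: 20 × √2 = 28.3.

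**Step 6: medians against the paired effect.** Take five invented patients with 1, 2, 10, 11, 12 before and 3, 4, 9, 13, 14 after. The medians go from 10 to 9, a fall of 1. The paired changes are +2, +2, −1, +2, +2, and their Hodges-Lehmann estimate is +2.

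**The case against.** The presentation sentence is descriptive. It does not forbid an estimate or an interval, and the section also plans ANOVA and linear regression, which produce both. The variables it covers could include within-patient changes, since the plan says that changes will be assessed. Nothing fails in data collection or in the chosen test, and an interval can be computed later from the same data.

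Much of this stands. A reader might infer that the plan reduces its results to significant or not significant; the documents do not say so. But the regression models are planned for covariates, where indicated, and no estimate or interval from them is promised. A range of changes would still not show precision.

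A reader might also infer that any nonsignificant result would rule out a 5% effect. It would not. Even with 128 complete pairs and SD 20, about 36% of nonsignificant trials with no true effect would leave +5 or −5 inside the interval. Nor is the range fairly called 30 times the uncertainty: that sets a full range against a half-width, and the like-for-like figure is about 15.

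Finally, the trial is nonrandomized, the direction of the switch follows prior habit, and the plan says that order is left uncontrolled. A narrow interval would therefore not establish that timing has little effect.

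**Conclusion.** The point holds as a reporting weakness. The one stated presentation rule for the main outcomes shows neither precision nor the within-patient difference, and nothing else in the documents fills the gap. The validity of the signed-rank test is not affected.

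On the plan's own figures the unreported interval would be informative: about ±3.5 points against a 5-point target, with roughly a 60% chance of excluding that target if timing has no effect. This rests on 20 being the SD of paired differences, on 128 complete pairs and on roughly normal differences. It weakens quickly with dropout or a larger SD, and if the SD is 28.3 the chance is about 5%. Where the target cannot be excluded, the interval is still what tells the reader so.

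The statement applies only to the 5-point target. The effect size of 0.1 in Study and Data Analysis equals 0.1 × 20 = 2 points on this scale, and an interval of ±3.5 cannot exclude it.

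**What to change.** Replace the presentation rule in Study and Data Analysis with text to this effect:

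- **Continuous and score outcomes** (metabolites, cytokines, other laboratory values, IBDQ, Harvey Bradshaw): give the median with 25th and 75th percentiles at each dosing time. Report the Hodges-Lehmann estimate of the within-patient morning-minus-evening difference, signed the same way for every patient whichever way they switched, with its 95% confidence interval from the signed-rank procedure.
- **Interpretation:** read the interval against the planning effects in Power and Sample Size and in Study and Data Analysis, stating the scale of each. State also whether the SD of 20 is that of paired differences.
- **Ratios:** if a ratio is wanted for metabolites or cytokines, run both the signed-rank test and the interval on log values. The 3.5-point half-width does not carry over to that scale.
- **Remission and complications:** report as paired proportions or counts.
- **Limit:** state that the interval shows precision only and does not remove the uncontrolled order effects.

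The cost is a little more analysis work. No further patients or measurements are needed. On the original scale the interval comes from the test already planned; a ratio would also move that test to logs, so this should be settled before analysis.
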